10.4. Statistical Analyses

10.4.1. Efficacy Analyses

All efficacy analyses will be performed on the mITT Population.

Endpoint	Statistical Analysis Methods
Primary	The primary endpoint proportion of subjects with loss of asthma control will be analyzed using both Bayesian and Frequentist methods. A subject is deemed to have met the endpoint of loss of asthma control if they meet the criteria for any of the components of the definition of loss of asthma control.
	The posterior probabilities that the ratio of the proportion of subjects with loss of asthma control on GSK3772847 compared with placebo is less than 1.0, 0.75, 0.5 and 0.2 (i.e. a 0%, 25%, 50% and 80% reduction) will be calculated analytically assuming a non-informative prior. This will be supported by an estimate of the ratio with a 95% credible interval. Results will also be presented for the two eosinophils strata separately.
	In addition, the proportion of participants with loss of asthma control will be analyzed using logistic regression allowing for baseline eosinophils strata. The odds ratio, 95% CI and p-value for the comparison of GSK3772847 with placebo will be presented.
	Results will also be presented for the two eosinophils strata separately by fitting a separate model with an additional term for eosinophil strata by treatment interaction. The effect of eosinophils as a continuous covariate will also be examined in a separate-logistic regression model.
	 Missing data will be handled using the following methods: 1) The loss of asthma control will be set to missing for participants who withdraw from IP prior to Week 16 for reasons other than loss of asthma control 2) A sensitivity analysis will be performed where participants who withdraw from IP prior to Week 16 for reasons other than loss of asthma control will have the endpoint set to loss of control
Secondary	The following secondary endpoints will be analyzed using the same statistical analysis as described for the primary endpoint: • Proportion of participants with a clinically significant asthma exacerbation

Endpoint	Statistical Analysis Methods
	 (requiring OCS and/or hospitalisation) Proportion of participants with Pre-bronchodilator FEV1 decrease from Baseline (measured at the end of Run-in) >7.5 % Proportion of participants with Inability to titrate inhaled corticosteroid
	 according to the pre-defined schedule (Section 5.1) Proportion of participants with ACQ-5 score increase from Baseline (measured at the end of Run-in) ≥0.5 point. Proportion of participants with a clinically significant asthma exacerbation or inability to titrate ICS according to the pre-defined schedule. In these analyses, the endpoint will be set to missing for participants who withdraw from IP prior to Week 16 for reasons other than loss of asthma control.
	Time to loss of asthma control will be analyzed using Kaplan-Meier analysis. Percentiles for time to loss of control will be presented for both treatment groups, along with graphical survival plots. Any early withdrawals from IP that did not experience loss of control will be censored. Results will be presented for both of the two eosinophil strata separately, and combined.
	The following endpoints will be analyzed using repeated logistic regression. This analysis will be repeated including an additional term for eosinophil strata by treatment by visit interaction to provide estimates for the two eosinophil strata separately:
	 Proportion of ACQ-5 responders (a ≥0.5 point improvement from baseline at Week 16) Proportion of SGRQ responders (at least a 4 unit improvement from
	baseline at Week 16 These analyzes will be performed using two different methods for handling missing data:
	If endpoint at a visit is missing then the responder status is set to missing
	2) If endpoint at a visit is missing and the endpoint is also missing at all subsequent visits then the responder status is set to non-responder. The odds ratio, 95% CI and p-value for the comparison of GSK3772847 with placebo will be presented for all models.
	Mixed model repeated measures will be used to analyze the following endpoints. The baseline value of each endpoint will be included along with baseline*visit and treatment*visit interactions. Treatment differences, 95% confidence intervals and p-values will be presented.
	 Change from baseline in ACQ-5 absolute score Change from baseline in SGRQ total score Change from baseline in Pre-bronchodilator FEV1
	Change from baseline in FeNO This analysis will be repeated including an additional term for eosinophil

Endpoint	Statistical Analysis Methods
	strata by treatment by visit interaction to provide estimates for each eosinophil strata separately. No adjustment will be made for missing data.
	Further information on how the following endpoints will be analyzed will be described in the report and analysis plan: • Hospitalisation or ER visit during the study treatment period • Morning and evening PEF • Daily asthma symptom score • Rescue medication use (albuterol/salbutamol): number of occasions per day • Night-time awakenings due to asthma symptoms requiring rescue medication
	Any changes to the planned analysis methods will be documented in the reporting and analysis plan. Details of subgroup analyses for the primary and secondary endpoints will be described in the reporting and analysis plan.
Exploratory	Will be described in the reporting and analysis plan

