5. STUDY DESIGN

5.1. Overall Design

This is a Phase IIa, multicenter, randomized, placebo-controlled, double-blind, stratified, parallel group study.

There will be a 2-week Run-in period following Screening (Visit 1). Eligible participants will be randomized at the end of the Run-in period (Visit 2). Randomization will be stratified based on participants' baseline peripheral blood eosinophil count aiming for at least 30% of participants with eosinophil count <150 cells/ μ L, which is measured at Screening. In order to achieve the stratification balance, as a result of participants' eosinophil count it may be necessary to withdraw participants from the study during the Run-in period.

When required, a pre-screening visit (Visit 0) can be scheduled up to 2 weeks prior to Screening (Visit 1). The pre-screening visit (Visit 0) can also occur on the same day as the Screening visit (Visit 1). Participants who meet the eligibility criteria at Screening (Visit 1) will withdraw their regular ICS/ long-acting beta-2-agonists (LABA) treatment for asthma and enter a two-week Run-in period during which they will receive open label background therapy of fluticasone propionate (FP)/salmeterol (Sal) 500/50 mcg BID. At

the end of the Run-in period at Visit 2 (Week 0), participants who meet pre-defined randomization criteria (Section 6.3) will be randomized in a 1:1 ratio to enter a double-blinded Treatment Period and receive the following study treatment every 4 weeks for 12 weeks (Week 0, 4, 8 and 12) while initially remaining on the open label background therapy of FP/Sal 500/50 mcg BID at Randomization:

- GSK3772847 administered intravenously or
- Placebo administered intravenously

[figure not shown]

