10. STATISTICAL CONSIDERATIONS

10.1. Hypotheses

The primary null hypothesis (H_0) for this study is that the ratio of the proportions of subjects with loss of asthma control from randomization to Week 16 between GSK3772847 and placebo is unity.

$$H_0 \colon \frac{Proportion\ with\ loss\ of\ asthma\ control\ at\ Week\ 16\ on\ GSK3772847}{Proportion\ with\ loss\ of\ asthma\ control\ at\ Week\ 16\ on\ Placebo} = 1$$

The alternative hypothesis (H_1) for this study is that the ratio of the proportions of subjects with loss of asthma control from randomization to Week 16 between GSK3772847 and placebo is not unity.

$$\textit{H}_{1} : \frac{\textit{Proportion with loss of asthma control at Week 16 on GSK3772847}}{\textit{Proportion with loss of asthma control at Week 16 on Placebo}} \neq 1$$

The hypothesis will be tested by calculating the posterior probability that the ratio of the proportion of subjects with loss of asthma control on GSK3772847 compared with placebo is less than 1.0, 0.75, 0.5 and 0.2 (i.e. a 0%, 25%, 50% and 80% reduction) and supported by an estimate of the ratio with a 95% credible interval. A non-informative prior will be used.

Although the success of the study will be assessed by calculating posterior probabilities of the treatment effect reaching various thresholds and not statistical significance, a frequentist analysis will also be performed testing the above hypothesis.

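### The posterior that decides success names no adjustment for the eosinophil randomisation stratum, and the only frequentist estimate is an odds ratio although the hypothesis and thresholds are ratios of proportions

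*Protocol*

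**What the plan says.** Section 5.1 reads "Eligible participants will be randomized at the end of the Run-in period (Visit 2). Randomization will be stratified based on" the peripheral blood eosinophil count taken at Screening, with a target of at least 30% of participants below 150 cells/µL.

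Section 10.1 states the null hypothesis as follows: "the ratio of the proportions of subjects with loss of asthma control from randomization to Week 16 between GSK3772847 and placebo is unity". It then says that "the success of the study will be assessed by calculating posterior probabilities of the treatment effect reaching various thresholds and not statistical significance", and that "a frequentist analysis will also be performed testing the above hypothesis".

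Section 10.4.1 gives the two primary analyses:

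- **Bayesian.** Posterior probabilities that the ratio is below 1.0, 0.75, 0.5 and 0.2 "will be calculated analytically assuming a non-informative prior". "This will be supported by an estimate of the ratio with a 95% credible interval". Results are also to be shown for each eosinophil stratum.
- **Frequentist.** The outcome is "analyzed using logistic regression allowing for baseline eosinophils strata. The odds ratio, 95% CI and p-value for the comparison" with placebo are to be presented. A treatment-by-stratum interaction model and a model with continuous eosinophils follow.

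The same section applies this pair of analyses to five secondary proportion endpoints. For the mixed models it says "The baseline value of each endpoint will be included along with baseline*visit and treatment*visit interactions". Stratum is named there only in a repeat analysis, as a three-way interaction with treatment and visit.

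**The concern.** Two features of the primary analysis do not line up.

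1. **Adjustment.** The allocation is stratified and the supporting model adjusts for the stratum. The overall posterior, which carries the decision, has no such provision in the text. If the stratum predicts loss of control and is left out, the posterior spread includes between-stratum variation that the design has already balanced, so the deciding analysis is less precise than it could be.

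2. **Effect measure.** Hypotheses, thresholds, the Bayesian estimate and the reduction column of Table 4 are all on the ratio of proportions. The one frequentist estimate is an odds ratio, conditional on stratum. With loss of control expected in 44% of the placebo arm, the two measures are far apart, and the odds ratio always looks the more favourable when treatment works. A team wanting a stratum-adjusted estimate to set beside the thresholds would have none on the right scale.

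**Working it through.** **Inputs from the protocol.** 70 evaluable per arm, 1:1 allocation, two-sided 5%, placebo rate 44%, active rate 22% for 80% power, and a rejection boundary of 28% on active (section 10.2). The low stratum is taken at its 30% minimum (section 5.1). The 31% printed beside the 28% boundary in section 10.2 is not used here.

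**Reproducing Table 4.** Pooled-variance formula without continuity correction, 44% v 22%:

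power = Φ{[0.22 − 1.96·√(2·0.33·0.67/70)] / √(0.44·0.56/70 + 0.22·0.78/70)} = Φ{(0.22 − 0.156)/0.0773} = 79.7%.

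Exact enumeration of the same test gives 80.3%, so the stated 80% stands. The rejection boundary also reproduces: the critical active rate is 28.1%. Neither figure depends on this point.

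**Ratio against odds ratio.** OR = [p₁/(1−p₁)] / [p₀/(1−p₀)].

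- 44% v 22%: ratio 0.22/0.44 = 0.50; OR (0.22/0.78)/(0.44/0.56) = 0.36.
- 44% v 28%: ratio 0.28/0.44 = 0.64; OR (0.28/0.72)/(0.44/0.56) = 0.49. A 36% lower risk appears as odds roughly halved.
- Thresholds at 44% placebo: 1.0, 0.75, 0.5 and 0.2 on the ratio correspond to 1.0, 0.627, 0.359 and 0.123 on the odds ratio.
- The conversion moves with the placebo rate. Over an assumed range of 30% to 60%, a ratio of 0.5 corresponds to an odds ratio of 0.41 to 0.29.

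Only the value 1 means the same on both scales.

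**Cost of leaving stratum out of the posterior.** Simulation with 4,000 trials per setting, 21 + 49 per arm (30% of 70 = 21). The protocol does not give the following, so they are assumptions: Jeffreys priors, success if Pr(ratio < 1) exceeds 0.975, balanced strata, and the placebo rates shown as low/high stratum. The stratified version draws stratum rates from their own posteriors and weights them 0.3 and 0.7.

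| Placebo rates | False success, unstratified v stratified | Success at ratio 0.5, unstratified v stratified |
|---|---|---|
| 44%/44% | 0.025 v 0.026 | 0.800 v 0.805 |
| 30%/50% | 0.024 v 0.026 | 0.804 v 0.812 |
| 20%/54% | 0.018 v 0.025 | 0.817 v 0.834 |

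The differences in success probability are 0.5, 0.8 and 1.7 points. The first row cannot be a prognostic gain, because stratum carries no information there. In the last row the mean posterior SD of the log ratio at ratio 0.5 falls from 0.268 to 0.255. Unstratified false success does not exceed 0.025 in any setting.

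**The case against.** The strongest objection is that the protocol never says the overall posterior is unadjusted. A reader might infer that it rests on crude pooled proportions, or that the Bayesian analysis ignores the stratum. The text supports neither. An analytical calculation does not rule out stratum weights, the detail could sit in the analysis plan, and Bayesian results by stratum are required. What stands is narrower: section 10.4.1 attaches the stratum to the logistic model and not to the overall posterior, in adjoining paragraphs of a primary method that the protocol itself fixes.

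A reader might also infer that the logistic analysis tests the wrong hypothesis. It does not: the odds ratio equals 1 exactly when the ratio of proportions equals 1, so the p-value is valid for the null in section 10.1. Nor does the protocol set the odds ratio against the 0.75, 0.5 or 0.2 thresholds, which belong to the posterior and come with their own ratio estimate. The misreading is a risk, not something planned.

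Finally, a reader might infer that the mixed models exclude stratum. The sentence on their terms names no treatment or visit main effect either, so it is a partial list, and silence about stratum does not show exclusion.

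The objection that the efficiency loss is small and in the safe direction is correct, and it limits the weight of the point.

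**Conclusion.** The point holds as a low-cost improvement, not as a flaw that threatens validity. The effect-measure mismatch is plain in the text and its size follows from the protocol's own rates: 0.50 against 0.36 at the planning assumption, 0.64 against 0.49 at the rejection boundary. It affects estimation and reading, not the test of no effect.

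The stratum half is a gap in what is named for the deciding analysis. If the posterior is in fact unadjusted and stratum is prognostic, the result is mildly conservative and unbiased. The loss is about 0.5 to 2 points of success probability, with false success between 0.018 and 0.025. Those figures rest on the assumed prior, cut-off, 30% low-stratum share and stratum-specific placebo rates. They concern only the threshold of 1.0; the other three were not simulated. The conversions do not depend on those assumptions.

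**What to change.** Amend the primary analysis in section 10.4.1, or settle it in the analysis plan before unblinding:

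1. Compute the overall posterior within eosinophil strata and combine with fixed weights w (for example, each stratum's share of the analysed participants, the same in both arms): standardised ratio = Σw·p(active) / Σw·p(placebo). Use this one ratio for all four thresholds and its 95% credible interval, and state the prior used per stratum.
2. From the logistic model, report a stratum-standardised ratio of proportions with 95% CI beside the odds ratio. Carry this and item 1 over to the five secondary proportion endpoints that use the same analysis.
3. Name stratum as a main effect in the mixed models and the repeated logistic models.

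Adjusting the primary model for baseline ACQ-5 and FEV1 is optional.

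The cost is a few sentences and some code, with no new data or visits. The one drawback is that the overall posterior is no longer a single closed-form expression and needs simulation or numerical integration.

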4. OBJECTIVES AND ENDPOINTS

	Objectives	Endpoints
Pri	mary	
•	To evaluate the efficacy of GSK3772847, compared with placebo, administered intravenously every 4 weeks for 12 weeks (Week 0 – Week 12, 4 doses in total) in participants with moderately severe asthma.	Primary – Proportion of participants with loss of asthma control over Weeks 0-16 where 'loss of asthma control' is defined as at least one of the following: • Asthma Control Questionnaire (ACQ-5) score increase from baseline (measured at the end of Run-in) ≥0.5 point or • Pre-bronchodilator Forced expiratory volume in 1 second (FEV1) decrease from baseline (measured at the end of Run-in) >7.5 % or • Inability to titrate inhaled corticosteroid according to the pre-defined schedule (Section 5.1) or • A clinically significant asthma exacerbation (requiring oral corticosteroid [OCS] and/or hospitalisation).
Sec	condary	
•	To evaluate other aspects of efficacy of GSK3772847 compared with placebo in participants with moderately severe asthma.	 Other efficacy endpoints (at or by Week 16): Proportion of participants with a ≥0.5 point. ACQ-5 score increase from baseline. Proportion of participants who have prebronchodilator FEV1 decrease from baseline (measured at the end of Run-in) >7.5 %. Proportion of participants where inhaled corticosteroids (ICS) cannot be titrated in accordance with the pre-defined schedule. Proportion of participants who have a significant asthma exacerbation (requiring OCS and/or hospitalisation).

Objectives	Endpoints

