6.3. Randomization Inclusion Criteria

At the end of the Run-in period (Visit 2), study participants must fulfil the following additional criteria in order to be randomized into the study and enter the treatment period:

CONFIDENTIAL

- 1. Asthma Control Questionnaire (ACQ): ACQ-5 score ≥ 1 and ≤ 4 at Visit 2.
- 2. **eDiary Compliance:** Compliance with completion of the eDiary reporting defined as completion of all questions/assessments on ≥4 of the last 7 days during the run-in period.

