10.2. Sample Size Determination

The study will randomize 74 participants per treatment arm with the aim of having 70 evaluable participants per arm. For the purpose of this study an evaluable participant is defined as a participant who completes the Week 16 clinic visit whilst remaining on IP or who withdraws from IP having met the primary endpoint. See Section 10.4.1 for how subjects who withdraw early from IP for reasons other than loss of asthma control are handled in the analysis.

In addition to testing the hypothesis in the overall population, the study will randomize a sufficient number of participants to evaluate trends in pre-defined subgroups (e.g. eosinophil strata).

The true proportion of participants that would experience a loss of asthma control on each treatment is unknown. However in a similar study of Dupilumab compared with placebo, the proportion of participants with loss of control were 6% and 44% for Dupilumab and placebo respectively. Table 4 gives the power to detect a statistically significant difference (at the two-sided 5% level) between the two treatments assuming the true proportion with loss of control on placebo is 44% and the true proportion with loss of control on active is 6%, 11%, 19% and 22% [Fleiss, 2003].

Table 4 Table of Power Achievable for Different Treatment Comparisons using N=70 per arm calculated using PASS

True proportion on Placebo	True proportion on GSK3772847	Reduction	Power
44%	6%	86%	> 99%
44%	11%	75%	> 99%
44%	19%	57%	90%
44%	22%	50%	80%

Assuming the true proportion with loss of control on placebo is 44%, then with 70 evaluable participants per arm, the study will have at least 80% power to detect a statistically significant difference between treatments assuming the true proportion with loss of control on GSK3772487 is at most 22% (Table 4).

With 70 evaluable participants per arm and assuming the true proportion with loss of control on placebo is 44%, the smallest observed difference that would lead to rejection of the null hypothesis (minimum detectable effect) is 31% corresponding to a proportion with loss of control on GSK3772847 of 28%.

There is a single primary endpoint so no adjustments are required for multiplicity.

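### The supportive logistic model for loss of asthma control adjusts only for eosinophil stratum; adding ACQ-5 and FEV1 from Visits 1 and 2 would be a cheap, modest and conditional efficiency gain

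*Protocol*

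**What the plan says.** Section 10.1 sets the decision rule: "the success of the study will be assessed by calculating posterior probabilities of the treatment effect reaching various thresholds and not statistical significance". Section 10.4.1 defines the posterior probabilities for the ratio of proportions, which "will be calculated analytically assuming a non-informative prior"; no covariate is mentioned. The frequentist analysis follows as an addition: "the proportion of participants with loss of asthma control will be analyzed using logistic regression allowing for baseline eosinophils strata", reported as an odds ratio with its interval and p-value.

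Section 4 defines the composite from four components. One is an ACQ-5 rise of at least 0.5 from the end of run-in. Another is "Pre-bronchodilator Forced expiratory volume in 1 second (FEV1) decrease from baseline (measured at the end of Run-in) >7.5" per cent. The remaining two are inability to titrate the inhaled steroid and a clinically significant exacerbation.

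Both measures exist at two pre-treatment visits. ACQ-5 is an entry criterion at Screening (Section 6.1) and again before randomization, "ACQ-5 score ≥ 1 and ≤ 4 at Visit 2" (Section 6.3). Pre-bronchodilator FEV1 is checked at Visit 1 (Section 6.2) and Visit 2 (Section 6.4).

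For the mixed models of continuous ACQ-5, SGRQ, FEV1 and FeNO, Section 10.4.1 does adjust: "The baseline value of each endpoint will be included along with baseline*visit and treatment*visit interactions".

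**The concern.** A participant whose single Visit 2 ACQ-5 happens to be low, or whose Visit 2 FEV1 happens to be high, is more likely to cross +0.5 points or −7.5% later through regression to the mean. The chances are many: ACQ-5 is weekly, and spirometry is scheduled at eight visits after baseline. The Visit 2 value, and its distance from the Visit 1 value, therefore carry some information about the outcome by the way the endpoint is built. Leaving them out of the analysis of the composite, while adjusting the continuous versions of the same measures, gives up whatever power that information could buy. The design has no slack to spare: 22% on active treatment is the point at which planned power is 80%.

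**Working it through.** **Inputs from Section 10.2.** "The study will randomize 74 participants per treatment arm with the aim of having 70 evaluable participants per arm"; placebo rate 44%; active rate 22%, 19%, 11% or 6%; "power to detect a statistically significant difference (at the two-sided 5% level) between the two treatments".

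**Step 1: reproduce Table 4.** With pooled variance under the null and no continuity correction, power = Φ[(d − 1.96·s0)/s1], where s0 = √(2p̄(1−p̄)/n) and s1 = √((p1(1−p1)+p2(1−p2))/n).

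At 44% versus 22%: d = 0.22, p̄ = 0.33, s0 = √(0.4422/70) = 0.0795, s1 = √(0.4180/70) = 0.0773. Power = Φ[(0.22 − 0.1558)/0.0773] = Φ(0.831) = 79.7%. At 19% the result is 89.8%, and both other rows exceed 99%. The table matches with no covariate, so the omission breaks no stated figure.

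**Step 2: what baseline terms do in the logistic model.** The protocol gives no prognostic strength, so it is varied here. Marginal rates were held at 44% and 22% with 70 per arm. A treatment-plus-stratum model was compared with the same model plus a baseline score and one uninformative term (5000 runs per row; simulation error about √(0.8×0.2/5000) = 0.6 points).

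| Assumed odds ratio per SD of baseline score | Power without | Power with | SE of log odds ratio, without → with | Change in variance of standardised risk difference |
|---|---|---|---|---|
| 1.0 | 80.1% | 79.8% | 0.384 → 0.391 | +1.6% |
| 1.25 | 80.1% | 80.4% | 0.385 → 0.394 | +0.2% |
| 1.5 | 78.5% | 79.4% | 0.385 → 0.399 | −1.8% |
| 2.0 | 80.1% | 83.3% | 0.384 → 0.414 | −7.5% |
| 2.5 | 80.2% | 85.0% | 0.385 → 0.430 | −11.1% |
| 3.0 | 78.8% | 86.7% | 0.384 → 0.446 | −17.0% |

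Power rises while the SE of the log odds ratio also rises, because the adjusted odds ratio is a conditional quantity that moves further from 1 (mean log odds ratio −1.049 to −1.172 at an odds ratio of 2.0 per SD). The variance reduction shows only on the standardised scale.

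**Step 3: build the endpoint from noisy visits.** Assumed: true ACQ-5 SD 0.7, eight post-baseline visits, 70 per arm, rates calibrated to 44% and 22%, 3000 runs.

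| Within-person noise (ACQ-5 SD; FEV1, log scale) | Stratum only | + Visit 2 values | + Visits 1 and 2 |
|---|---|---|---|
| 0.10; 0.02 | 79.4% | 79.7% | 80.0% |
| 0.15; 0.025 | 79.8% | 79.8% | 81.8% |

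Visit 2 values alone add 0.0 to 0.3 points; both visits add 0.6 to 2.0. At noise of 0.20 and 0.03, noise alone already gives a 31% event rate, so 22% on active treatment cannot be reached. Larger gains obtained by assuming more noise therefore sit badly with the planned rates in this model.

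**Step 4: the cost side.** Expected events are 70×0.44 + 70×0.22 = 30.8 + 15.4 = 46.2. Treatment, stratum and four covariates make six terms, or 46.2/6 = 7.7 events per term. If all four covariates were useless, a rough variance inflation is 4/140 = 2.9%. Power becomes Φ[(0.22/√1.029 − 0.1558)/0.0773] = 78.6%, about one point lower at worst.

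**The case against.** Several stronger readings are tempting, and the documents do not support them.

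- A reader might infer that the decisive analysis is inefficient because its model omits covariates. Section 10.1 puts the decision on the posterior probabilities; the logistic regression is supportive. Extra terms in it change no decision unless a standardised ratio is carried into the Bayesian calculation.
- A reader might infer that precision of the reported odds ratio is lost. The reverse holds: its standard error increases with adjustment.
- A reader might infer a gain to about 90% power. Under a linear variance-factor approximation, that needs a multiple correlation of 0.5 between baseline values and the event, for which neither the protocol nor the visit-level checks give support.
- A reader might infer bias from chance baseline imbalance. Randomization and the interval already account for it, and adjustment for the stratification factor is valid.

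The case against acting at all also has substance. Visit 1 is on the participant's own ICS/LABA and Visit 2 follows two weeks of study FP/salmeterol. Spirometry must be repeatable at Visit 1 but not from Visit 2 (Section 9.1.3.1). The difference between visits is therefore not pure noise. Two of the four components are not changes from these baselines. About 46 events is not many for six terms. Section 10.4.1 also allows changes to be documented in a reporting and analysis plan that is not shown.

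These points keep the gain modest. They do not remove it: a covariate can be prognostic whatever the source of the difference, the unadjusted result is kept, and the covariate set is something that the protocol itself states rather than leaves open.

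**Conclusion.** The planned analysis is valid and contradicts nothing. It is a missed, low-cost efficiency improvement. Expected size: roughly 0 to 1 power point from Visit 2 values alone, and roughly 0 to 5 points from both visits under moderate assumptions (odds ratio per SD up to 2.5, or the visit-level scenarios). The 8-point gain at an odds ratio of 3.0 per SD needs a stronger assumption than anything here justifies. If the covariates are uninformative the loss is negligible: 0.3 points in simulation with two added terms, and about one point at worst with four. All of this rests on assumed prognostic strength and measurement noise, because the protocol gives neither. The benefit applies to power and to the standardised effect, not to the standard error of the odds ratio.

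**What to change.** Before unblinding, amend Section 10.4.1 or fix in the reporting and analysis plan:

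1. For the composite endpoint, the logistic model includes treatment, eosinophil stratum, and ACQ-5 and pre-bronchodilator FEV1 at Visits 1 and 2 as continuous covariates. The Visit 2 value plus the Visit 1 to Visit 2 difference is an equivalent form.
2. From that model, report the standardised (marginal) ratio of proportions with its interval, and the posterior probabilities at the four planned thresholds based on it.
3. Keep the unadjusted Bayesian ratio beside it, and state in advance which of the two the success assessment uses.
4. Limit the fuller model to the composite. Section 10.4.1 applies the primary analysis to the component endpoints as well, and exacerbation alone cannot have more events than the composite, so those should keep the stratum-only model.

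The cost is wording and programming, with no new visits or data. The downsides are four more model terms on about 46 expected events, and an additional posterior that rests on a model-based estimate instead of raw counts.
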